
6.2 Second Course Phase (Retreatment ONLY)

Trial Period:	SECOND COURSE PHASE: Treatment Cycles ^a								End of Treatment	Post-Treatment			
	Treatment Cycle/Title:	1	2	3	4	To be repeated beyond 8 cycles				DC	Safety Follow-up ^b 30 days from last dose (±3 days)	Follow Up Visits ^c Every 9 weeks (±7 days)	Survival Follow-Up ^d Every 12 weeks (±7 days)
Scheduling Window (Days):			±3	±3	±3	±3	±3	±3	±3				
Administrative Procedures													
Eligibility Criteria ^e	X												
Concomitant Medication Review ^f	X	X	X	X	X	X	X	X	X	X	X		
Trial Treatment Administration	X	X	X	X	X	X	X	X	X				
Subsequent Anticancer Therapy Status											X	X	
Survival Status ^g	←-----→									←-----→			X
Clinical Procedures/Assessments													
AE/SAE Monitoring	X	X	X	X	X	X	X	X	X	X	X ^h	X ^h	
Full Physical Examination ⁱ	X									X			
Directed Physical Examination ⁱ		X	X	X	X	X	X	X	X				
Vital Signs and Weight	X	X	X	X	X	X	X	X	X	X			
ECOG Performance Status	X	X	X	X	X	X	X	X	X ^j	X			
Laboratory Procedures/Assessments: analysis performed by LOCAL laboratory													
PT/INR and PTT/aPTT	X ^k												
CBC with Differential ^l	X ^k	X	X	X	X	X	X	X	X	X	X ^m		
Comprehensive Chemistry Panel ^l	X ^k	X	X	X	X	X	X	X	X	X	X ^m		
T3, FT4 and TSH ^l	X ^k		X ⁿ		X		X		X	X	X ^m		
Urinalysis ^l	X ^k		X ⁿ		X		X		X	X	X ^m		
Total Testosterone ^l	X ^k			X ^o				X	X	X			
Laboratory Procedures/Assessments: analysis performed by CENTRAL laboratory													
Tumor Marker Assessment (PSA) ^p	X			X			X		X	X		X ^c	
Efficacy Measurements													
Tumor Imaging ^p (CT/MRI/bone scan)	X ^q			X			X		X ^r	X		X ^c	

Trial Period:	SECOND COURSE PHASE: Treatment Cycles ^a								End of Treatment	Post-Treatment			
	Treatment Cycle/Title:	1	2	3	4	To be repeated beyond 8 cycles				DC	Safety Follow-up ^b	Follow Up Visits ^c	Survival Follow-Up ^d
Scheduling Window (Days):			±3	±3	±3	±3	±3	±3	±3				

Abbreviations: AE = adverse event; aPTT = activated partial thromboplastin time; CBC = complete blood count; CT = computed tomography; DC = discontinuation; ECOG = Eastern Cooperative Oncology Group; FT4 = free thyroxine; INR = international normalized ratio; MRI = magnetic resonance imaging; PSA = prostate-specific antigen; PT = prothrombin time; PTT = partial thromboplastin time; SAE = serious adverse event; T3 = triiodothyronine; TSH = thyroid stimulating hormone.
 
a. All treatment cycles are 3 weeks ± 3 days.
 
b. If a subject initiates a new anti-cancer therapy within 30 days after the last dose of trial treatment, the 30-day Safety Follow-up visit must occur before the start of the new therapy. Once new anti-cancer therapy has been initiated the subject will move into survival follow-up.
 
c. Follow-up visits must occur every 9 weeks (63 days ±7 days) from the date of last dose of study treatment. In subjects who discontinue therapy without documented disease progression, every effort should be made to continue monitoring disease status by radiologic imaging (CT/MRI and bone scans) and PSA until: 1) the start of new anti-cancer treatment, 2) documented disease progression, 3) death or 4) the end of the study, whichever occurs first.
 
d. Survival follow-up begins 12 weeks from the time a subject experiences confirmed disease progression or starts a new anti-cancer treatment.
 
e. Subjects may restart trial treatment if they meet the criteria specified in Section 7.1.5.2.
 
f. Report new medications started during the trial and up to 30 days after last dose of trial treatment regardless of when the safety follow-up visit occurs. All medications related to reportable SAEs and events of clinical interest (ECIs) should be recorded as defined in Section 7.2.
 
g. After documented local site assessed disease progression, or the start of new anticancer treatment; contacts are approximately every 12 weeks by telephone. Updated survival status may be requested by the Sponsor at any time during the course of the study. Upon Sponsor notification, all participants who do not/will not have a scheduled study visit or study contact during the Sponsor defined time period will be contacted for their survival status (excluding participants that have a death event previously recorded).
 
h. Record all AEs (including ECIs) occurring up to 30 days after the last dose of trial treatment. SAEs must be recorded up to 90 days after the last dose of trial treatment or 30 days following cessation of treatment if the subject starts new anti-cancer treatment. Treatment related SAEs must always be reported.
 
i. A full physical exam will be performed prior to subject receiving first retreatment infusion and at treatment discontinuation; all treatment visits will include a directed physical exam.
 
j. Following Cycle 8, ECOG Performance Status will be performed at every other cycle (Cycles 10, 12, 14,...) and at treatment discontinuation.
 
k. Laboratory tests are to be performed within 10 days prior to subject receiving first retreatment infusion.
 
l. After Cycle 1, pre-infusion laboratory procedures may be conducted up to 72 hours pre-infusion.
 
m. Unresolved abnormal lab results associated with drug-related AEs should be followed until resolution.
 
n. Urinalysis and thyroid function testing are performed within 10 days prior to first retreatment infusion, every other cycle (Cycles 3, 5, 7,...), treatment discontinuation, and the safety follow-up visit.
													

Trial Period:	SECOND COURSE PHASE: Treatment Cycles^a								End of Treatment	Post-Treatment			
Treatment Cycle/Title:	1	2	3	4	To be repeated beyond 8 cycles				DC	Safety Follow-up ^b	Follow Up Visits ^c	Survival Follow-Up ^d	
Scheduling Window (Days):		±3	±3	±3	±3	±3	±3	±3	±3	At time of DC	30 days from last dose (±3 days)	Every 9 weeks (±7 days)	Every 12 weeks (±7 days)

o. Total testosterone will be done within 10 days prior to first retreatment infusion, every fourth cycle (Cycles 4, 8, 12,...) and at treatment discontinuation.
 
p. Imaging assessments (CT/MRI and bone scans) and PSA should be performed every 9 weeks (63 days ±7 days), at treatment discontinuation and during follow-up. The timing of these assessments should not be adjusted for dose delays or cycle starts.
 
q. Imaging assessment must be performed within 28 days prior to the subject receiving first retreatment infusion. Scans performed as part of routine clinical management are acceptable if they are of diagnostic quality and performed within 28 days prior to the first dose of retreatment.
 
r. If a scan was obtained within 4 weeks prior to treatment discontinuation, then another scan at discontinuation is not mandatory. Radiological evaluation should be repeated at treatment discontinuation in subjects discontinuing without confirmed disease progression (date of discontinuation ±4 weeks)
													

7.0 TRIAL PROCEDURES

7.1 Trial Procedures

The Trial Flow Chart - Section 6.0 summarizes the trial procedures to be performed at each visit. Individual trial procedures are described in detail below. It may be necessary to perform these procedures at unscheduled time points if deemed clinically necessary by the investigator.

Furthermore, additional evaluations/testing may be deemed necessary by the investigator and or the Sponsor for reasons related to subject safety. In some cases, such evaluation/testing may be potentially sensitive in nature (e.g., HIV, Hepatitis C, etc.), and thus local regulations may require that additional informed consent be obtained from the subject. In these cases, such evaluations/testing will be performed in accordance with those regulations.

7.1.1 Administrative Procedures

7.1.1.1 Informed Consent

The investigator or qualified designee must obtain documented consent from each potential subject or each subject's legally acceptable representative prior to participating in a clinical trial or Future Biomedical Research. If there are changes to the subject's status during the trial (e.g., health or age of majority requirements), the investigator or qualified designee must ensure the appropriate consent is in place.

7.1.1.1.1 General Informed Consent

Consent must be documented by the subject's dated signature or by the subject's legally acceptable representative's dated signature on a consent form along with the dated signature of the person conducting the consent discussion.

A copy of the signed and dated consent form should be given to the subject before participation in the trial.

The initial informed consent form, any subsequent revised written informed consent form and any written information provided to the subject must receive the IRB/ERC's approval/favorable opinion in advance of use. The subject or his/her legally acceptable representative should be informed in a timely manner if new information becomes available that may be relevant to the subject's willingness to continue participation in the trial. The communication of this information will be provided and documented via a revised consent form or addendum to the original consent form that captures the subject's dated signature or by the subject's legally acceptable representative's dated signature.

Specifics about a trial and the trial population will be added to the consent form template at the protocol level.

The informed consent will adhere to IRB/ERC requirements, applicable laws and regulations and Sponsor requirements.

7.1.1.1.2 Consent and Collection of Specimens for Future Biomedical Research

The investigator or qualified designee will explain the Future Biomedical Research consent to the subject, answer all of his/her questions, and obtain written informed consent before performing any procedure related to the Future Biomedical Research sub-trial. A copy of the informed consent will be given to the subject.

7.1.1.2 Inclusion/Exclusion Criteria

All inclusion and exclusion criteria will be reviewed by the investigator or qualified designee to ensure that the subject qualifies for the trial.

7.1.1.3 Subject Identification Card

All subjects will be given a Subject Identification Card identifying them as participants in a research trial. The card will contain trial site contact information (including direct telephone numbers) to be utilized in the event of an emergency. The investigator or qualified designee will provide the subject with a Subject Identification Card immediately after the subject provides written informed consent.

The subject identification card also contains contact information for the emergency unblinding call center so that a health care provider can obtain information about trial medication/vaccination in emergency situations where the investigator is not available.

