5.2.1.2 Dose Modification (Escalation/Titration/Other)

5.2.1.2.1 Pembrolizumab

Dose modification and toxicity management for immune-related AEs associated with pembrolizumab

AEs associated with pembrolizumab exposure may represent an immunologic etiology. These immune-related AEs (irAEs) may occur shortly after the first dose or several months after the last dose of pembrolizumab treatment and may affect more than one body system simultaneously. Therefore, early recognition and initiation of treatment is critical to reduce complications. Based on existing clinical trial data, most irAEs were reversible and could be managed with interruptions of pembrolizumab, administration of corticosteroids, and/or other supportive care. For suspected irAEs, ensure adequate evaluation to confirm etiology or exclude other causes. Additional procedures or tests such as bronchoscopy, endoscopy, or skin biopsy may be included as part of the evaluation. Based on the severity of irAEs, withhold or permanently discontinue pembrolizumab and administer corticosteroids. Dose modification and toxicity management guidelines for irAEs associated with pembrolizumab are provided in [Table 3](#).

Table 3 Dose Modification and Treatment Discontinuation Guidelines for Immune-related Adverse Events Associated with Pembrolizumab

General instructions:				

 1. Corticosteroid taper should be initiated upon AE improving to Grade 1 or less and continue to taper over at least 4 weeks. 2. For situations where pembrolizumab has been withheld, pembrolizumab can be resumed after AE has been reduced to Grade 1 or 0 and corticosteroid has been tapered. Pembrolizumab should be permanently discontinued if AE does not resolve within 12 weeks of last dose or corticosteroids cannot be reduced to ≤ 10 mg prednisone or equivalent per day within 12 weeks. 3. For severe and life-threatening irAEs, IV corticosteroid should be initiated first followed by oral steroid. Other immunosuppressive treatment should be initiated if irAEs cannot be controlled by corticosteroids. 				
irAEs	Toxicity grade or conditions (NCI CTCAE v4.0)	Action taken to pembrolizumab	irAE management with corticosteroid and/or other therapies	Monitor and follow-up

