- j. Record all AEs (including ECIs) occurring up to 30 days after the last dose of trial treatment. SAEs must be recorded up to 90 days after the last dose of trial treatment or 30 days following cessation of treatment if the subject starts new anti-cancer treatment. Treatment related SAEs must always be reported.

Trial Period:	Screening Phase	Treatment Cycles ^b								End of Treatment	Post-Treatment			
		1	2	3	4	To be repeated beyond 8 cycles					DC	Safety Follow-up ^c	Follow Up Visits ^d	Survival Follow-Up ^e
Treatment Cycle/Title:	Screening (Visit 1) ^a					5	6	7	8					
Scheduling Window (Days):	-42 to -1		±3	±3	±3	±3	±3	±3	±3	±3	At time of DC	30 days after last dose (±3 days)	Every 9 or 12 weeks (±7 days)	Every 12 weeks (±7 days)

- k. A full physical exam will be performed at screening and at treatment discontinuation; all treatment visits will include a directed physical exam.
- l. Height will be measured at screening only.
- m. Following Cycle 8, ECOG Performance Status will be performed at every other cycle (Cycles 10, 12, 14,...) and at treatment discontinuation.
- n. Laboratory procedures at screening are to be performed within 10 days prior to the first dose of trial treatment.
- o. After Cycle 1, pre-infusion laboratory procedures may be conducted up to 72 hours pre-infusion.
- p. Unresolved abnormal lab results associated with drug-related AEs should be followed until resolution.
- q. Urinalysis and thyroid function testing are done at screening, every other cycle (Cycles 2, 4, 6,...), treatment discontinuation, and the safety follow-up visit.
- r. Total testosterone will be done at screening, every fourth cycle (Cycles 4, 8, 12,...) and at treatment discontinuation
- s. Imaging assessments (CT/MRI and bone scans) and PSA should be performed every 9 weeks (63 days ±7 days) for the first year (through week 54), every 12 weeks (84 days ±7 days) in the second year, at treatment discontinuation and during follow-up. The timing of these assessments should not be adjusted for dose delays or cycle starts. For Cohorts 4 and 5, screening PSA by central results are required prior to allocation. PSA should be performed Q3W until Cycle 4.
- t. Pre-infusion (trough) PK and anti-pembrolizumab antibody (ADA) samples will be collected within 24 hours before infusion at Cycles 1, 2, 4, 6, and 8. To be collected from subjects in Cohorts 1 to 3 only.

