7.1.5.1 Screening

Approximately 42 days prior to enrollment, potential subjects will be evaluated to determine that they fulfill the entry requirements as set forth in Section 5.1. Visit requirements are outlined in Section 6.0 – Trial Flow Chart.

After providing main study consent subjects will be assigned a screening number. Subjects must sign the main study consent prior to submitting existing tissue samples and/or undergoing a new biopsy. Requirements pertaining to submission of tissue samples are found in Section 7.1.2.7.

Results of a test performed prior to the subject signing consent as part of routine clinical management are acceptable in lieu of a screening test if performed within the specified time frame.

Screening procedures are to be completed within 42 days prior to the first dose of trial treatment. The following procedures need to be performed within the specified time frames:

- Laboratory tests within 10 days prior to the first dose of trial treatment (unless otherwise noted in the protocol).
- ECOG within 10 days prior to the date of treatment allocation.
- Baseline imaging assessments by CT (or MRI) and bone scan within 28 days prior to the first dose of trial treatment.
- Prostate-Specific Antigen (PSA) tumor marker assessment within 28 days prior to the date of allocation.

Subjects may be rescreened after initially failing to meet the inclusion/exclusion criteria. Results from assessments performed during the initial screening period are acceptable in lieu of a repeat screening test if performed within the specified time frame and the inclusion/exclusion criteria is met.

The subject identification card will be updated with the screening number.

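### Flow chart 6.1 takes back the emergency Subject Identification Card at treatment discontinuation, while the subject is still in the trial and under SAE collection, and nothing provides for a card in Second Course

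*Protocol*

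**What the plan says.** **Purpose and issue of the card.** Protocol Section 7.1.1.3 says of the card: "The card will contain trial site contact information (including direct telephone numbers) to be utilized in the event of an emergency". It adds a call-center contact that a health care provider can use when the investigator cannot be reached. On issue it says: "The investigator or qualified designee will provide the subject with a Subject Identification Card immediately after the subject provides written informed consent". Section 7.1.5.1 adds only this: "The subject identification card will be updated with the screening number". Neither section mentions return of the card or a second issue.

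**Collection.** The only instruction to take the card back is in the Section 6.1 flow chart. Its Subject Identification Card row has a dispense mark at Screening and a collect mark at discontinuation (DC).

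**What continues after discontinuation.** Section 5.8.1 says that stopping treatment is not withdrawal from the trial. Section 5.2.1.2.1 says of late toxicity: "These immune-related AEs (irAEs) may occur shortly after the first dose or several months after the last dose of pembrolizumab treatment". Footnote j of the 6.1 chart sets the collection windows: "Record all AEs (including ECIs) occurring up to 30 days after the last dose of trial treatment", and "SAEs must be recorded up to 90 days after the last dose of trial treatment". Footnote j and Section 7.2.3.1 shorten the SAE window to 30 days if new anti-cancer therapy starts.

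**Second Course.** The Section 6.2 flow chart has no card row. Section 7.1.5.2.1 allows up to 17 further infusions, gives no card instruction, and refers the reader to Section 6.1 for visit requirements. There the only dispense mark is at Screening.

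**The concern.** The card exists so that someone who meets the subject in an emergency can see that he is in a trial and whom to call. The chart removes it at the point where three-weekly dosing visits stop, although the protocol itself names late immune-related toxicity and keeps SAE collection open. Retreatment is harder to explain as a deliberate choice. A subject whose card was collected at the end of the first course goes back on active treatment, and no instruction gives him another card.

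What is at stake is prompt contact between an outside physician and the site, and secondarily the completeness of SAE reports after treatment ends. No endpoint, analysis population or sample size depends on it.

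**Working it through.** There is no plan figure to reproduce. The check is of where the mark sits in the chart and of what the text covers.

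**1. Which visit collects the card.** Each row of the 6.1 chart has 13 cells: Screening (1), Cycles 1 to 8 (2 to 9), DC (10), Safety Follow-up (11), Follow-up Visits (12) and Survival Follow-up (13).

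| Row | Marked cells |
|---|---|
| Subject Identification Card | 1 (dispense), 10 (collect) |
| Full Physical Examination | 1, 10 |
| Vital Signs and Weight | 1 to 10 |
| Prior and Concomitant Medication Review | 1 to 11 |
| CBC with Differential | 1, 3 to 11 |

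Footnote k fixes the meaning of cells 1 and 10 in the physical examination row: "A full physical exam will be performed at screening and at treatment discontinuation; all treatment visits will include a directed physical exam". Rows that do include the 30-day visit carry a mark in cell 11. The card is therefore collected at the discontinuation visit, not at the 30-day Safety Follow-up.

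**2. What remains of the SAE window.** Let d be the number of days from the last dose to the discontinuation visit. The chart schedules that visit only at the time of discontinuation, so d is not given. The time in the SAE window without a card is 90 - d days, or 30 - d if new anti-cancer therapy starts (zero if d exceeds the window). Three assumed values show the range:

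| d (assumed) | No new therapy | New therapy started |
|---|---|---|
| 0 | 90 - 0 = 90 days | 30 - 0 = 30 days |
| 21 (one cycle) | 90 - 21 = 69 days | 30 - 21 = 9 days |
| 30 | 90 - 30 = 60 days | 30 - 30 = 0 days |

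The protocol's reference to several months has no stated length, so no figure is put on the period of possible late toxicity beyond Day 90.

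**3. Scheduled safety contact in that period.** The AE/SAE Monitoring row is marked at DC, Safety Follow-up and Follow-up Visits, but not at Survival Follow-up. Two groups differ:

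- Subjects who stop without progression keep visits every 9 or 12 weeks (6.1, footnote d).
- Subjects with confirmed progression move to telephone contact about every 12 weeks to establish survival status (7.1.5.3.1). If they have not started new therapy, the last scheduled AE contact is the 30-day visit. That leaves 90 - 30 = 60 days of the SAE window with none.

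**4. Second Course.** 17 infusions x 3 weeks = 51 weeks of treatment cycles, followed by the same post-treatment windows. Sections 6.2, 7.1.1.3, 7.1.5.1 and 7.1.5.2.1 contain no provision for a second card.

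**5. How many subjects.** Planned enrollment is about 370. That is an upper bound for step 2, since subjects who die on treatment are not affected. The number entering Second Course is not stated. Section 7.1.5.2.1 limits entry to subjects who stopped after a confirmed CR (with minimum exposure) or completed 35 administrations with stable disease or better, and who then progressed with no anti-cancer treatment in between.

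**The case against.** The strongest reply is that the card is one safeguard among several.

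- The subject receives a copy of the signed consent form (7.1.1.1.1), and nothing takes it back.
- The trial is open-label (5.2.3), so he knows he received pembrolizumab. The unblinding purpose of the call-center line has little force here.
- Section 10.3 notes the GCP recommendation to inform the primary physician, if the subject agrees.
- Section 7.1.5.3 requires a clinic visit at about 30 days, with a telephone call at Day 30 if that visit was early.
- Section 7.2.3.1 requires related SAEs that come to the investigator's attention to be reported at any time, including after Day 90.

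All of this stands, and it rules out several stronger conclusions that a reader might draw:

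- *The card is the only link to the site.* It is not, although the protocol does not present the consent copy as an emergency document.
- *SAEs will be missed.* The documents do not show this, and most routes of SAE capture do not use the card.
- *Late toxicity is likely to be seen first elsewhere.* No section says so. Section 5.2.1.2.1 says only that late events may occur.
- *Subjects are retreated without a card.* The text is silent on re-issue and does not forbid it, and a site may issue one.
- *Every subject loses the card for the full 30 or 90 days.* The gap starts at the discontinuation visit, which may follow the last dose, and the SAE window can close at 30 days.

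It can also be said that returning a trial card when treatment ends is an administrative choice. That does not answer the point. The chart states a rule, the rule takes effect while the subject is still a participant under SAE collection, and no section leaves the card with him or gives him another.

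**Conclusion.** The point holds as a minor safety gap and an inconsistency between the card's stated purpose and the chart. As written, the card is collected at treatment discontinuation. That leaves up to 90 days of the SAE window uncovered (up to 30 if new therapy starts), for at most about 370 subjects. The subset entering Second Course has no provision for a card for up to 51 weeks of retreatment and the windows after it.

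This rests on two things: the position of the collect mark, which footnote k corroborates through the physical examination row, and the absence of any re-issue text in the sections listed above. The documents do not allow the number of affected events to be estimated. No estimate, confidence interval or sample size changes.

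**What to change.** 1. In the 6.1 chart, remove the collect mark at DC. Let the subject keep the card until his participation ends, and at least through the 90-day SAE window.
2. Add a Subject Identification Card row to the 6.2 chart: check that the subject holds a card, or re-issue one, at Second Course Cycle 1.
3. In Section 7.1.1.3, state how long the card is held. In Section 7.1.5.2.1, state that it is checked or re-issued, and refer to Section 6.2 for Second Course visits.

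The cost is wording in two charts and two sections, and some cards that are not returned. No dose, visit, endpoint or analysis changes.
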